The current study will include prospectively collected data on patients with PsA treated in routine care who initiate a conventional synthetic- or biologic – disease modifying (cs/bDMARD) treatment due to active PsA.

Analysis objectives

Our overall scientific objective is to investigate pain profile in relation to arthritic US findings in patients with PsA, and to study the predictive value of pain profile and ultrasonographic scores on response to conventional synthetic or biologic disease modifying (cs/bDMARD) treatment.

Population

The study is designed as an exploratory, prospective observational study enrolling patients with PsA according to CASPAR criteria,[21] who initiate/switch b/csDMARDs in routine care due to active PsA. Patients complete an examination programme at baseline and after 4 months including interview, clinical, ultrasonic and para-clinical assessments as well as electronic questionnaires. The inclusion period was between 17th of September 2015 and 1st of June 2017. A flow chart (figure 1) depicts the eligibility and inclusion process.

Collected variables

Interview

Baseline

A physician (PH or CB) interviews patients regarding their PsA and psoriasis diagnoses, current and former medical treatments, demographic and lifestyle factors and known co-morbidities (physical and mental) according to the pre-specified protocol.[1] Variables of interest for are depicted in Table 1.

Follow-up

At follow-up the same physicians (PH or CB) register changes in medical treatments including reasons for withdrawal of cs/bDMARDs.

Patient reported outcome measures (PROMs)

Touchscreen questionnaires are used for completing PROMs at baseline (Table 1) and at follow-up.

The intensity of pain is assessed by a visual analogue scale (VAS) (0-100 mm). The WPI and PDQ are applied to assess the patient's pain profile; WPI[12] is applied to determines if the pain is widespread or not, and the PDQ[14,22] clarifies if nociceptive or neuropathic pain features are dominating. These measures are described in more details in a later section.

Four other disease related concepts are covered by PROMs (Table 1):

- Health related quality of life/disease impact is assessed by The Psoriatic Arthritis Impact of Disease (PsAID)[4] and the Dermatology Life Quality Index (DLQI).[23]
- Mental well-being/anxiety is assessed by Generalized anxiety disorder (GAD-10)[24] and the Medical Outcome Survey Short Form-36 mental health score (MOS SF-36 MH).[25]

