The inter- and intra-rater reliability for GAUS, GSAUS, GCUS will be quantified using the intraclass correlation coefficient (ICC).[41] ICC ranges between 0 (no reliability) and 1 (perfect reliability). Values <0.40 will be interpreted as poor reliability, 0.40 to 0.59 as fair reliability, 0.60 to 0.74 as good reliability and 0.75-1.00 as excellent reliability.[42] The ICC will be of the type ICC(2,1), i.e. based on a two-way random effects model estimating agreement with single measures.[41,43]

Treatment persistency and reasons for withdrawal

The total number and percentage of patients who continued treatment from baseline to follow-up will be reported for each pain profile (WP versus no WP). Among patients who stopped treatment during the observation period, reasons for withdrawal will be reported as either 1) adverse events or 2) lack of efficacy.

Primary analyses

The primary outcome is ACR20, coded as a binary variable. The co-primary predictors of interest are WP and GAUS, both coded as a binary variable. The primary analyses will be based on logistic regression models investigating if there is an association between ACR20 response and each of the primary predictors of interest (WP, GAUS). Furthermore, a test for interaction between GAUS and WP will be performed. Estimates will be reported from unadjusted and adjusted models, and the crude numbers of responders will be reported for each of the binary predictors. The adjusted models would ideally include all available factors that are expected to influence the result (hypothesis driven model), however, due to the relatively small sample size and risk of statistical overfitting, the models will only be adjusted for age (years) and gender (male/female). The design of the primary models is illustrated in Table 2.

Rationale for the selected confounders

Augmented pain processing seem to be more prominent in women compared to men[36,44], and it is possible that gender affects the odds of experiencing a treatment response[45-47], and hence may confound the relationship between WP pain profile (predictor) and response (outcome). Similarly, higher age may also by several pathways influence both the measures of the primary

predictors and the chance of achieving a treatment response. The primary model will not be adjusted by type of treatment received, due to risk of bias from indication for treatment.[48]

Secondary analyses

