Secondary analyses will include repeating the logistic regression models using the secondary outcomes (MDA, DAPSA 50% and PR improvement) for the primary predictors (WP and GAUS, both binary), as well as repeating the logistic regression model with ACR20 as outcome for the secondary predictors of interest (binary measures of PDQ, TPC, SJ/TJ GSAUS and GCUS). The number of responders (and corresponding percentage) will be reported for every predictor (all categorical). Furthermore, change in the domains of the updated OMERACT core outcome set according to WP and GAUS profile will be analysed, and scatter diagrams will be applied to study the relationship between continuous measures of WPI and GAUS at baseline and the change in DAS28-CRP and in DAPSA during the treatment period.

Handling of multiplicity and other data conventions

In all analyses, p-values < 0.05 will be considered statistically significant. No correction for multiple testing will be done; instead the results will be interpreted with caution in the context multiplicity.

Missing data and analysis population

The main analysis population will be defined as those who fulfilled the inclusion criteria (i.e. the intention-to-treat population). For the outcomes (follow-up visit), missing data will be imputed by a non-responder assumption (i.e. baseline observation carried forward).

An as-observed population will be defined as those for whom data have been observed and no imputation will be carried out.

A per-protocol population will be defined as those who have complete data on the variables used for the analysis (i.e. the response variable and the predictor variables) and who adhered to the assigned treatment during the observation period.

Sensitivity analyses

A sensitivity analysis will be conducted to study the value of the primary pain and ultrasound predictors on ACR20 response including the per-protocol population and as-observed population.

Programming

The analyses will be conducted using the statistical program R (version 3.3.3).[49]

The program code for the primary analyses in the statistical program R:

```

#Logistic regression, ACR20 response, WP, univariate
M1<-glm(ACR_response ~ WP, family=binomial)
anova(M1, test="Chisq")
summary(M1)

#Logistic regression, ACR20 response, WP, adjusted for gender and age
M1<-glm(ACR_response ~ WP + Gender + Age, family=binomial)
M1<-glm(ACR_response ~ Gender + Age, family=binomial)
anova(M1,M0, test="Chisq")
summary(M1)

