#Logistic regression, ACR20 response, GAUS, univariate
M1<-glm(ACR_response ~ GAUS, family=binomial)
anova(M1, test="Chisq")
summary(M1)

#Logistic regression, ACR20 response, GAUS, adjusted for gender and age
M1<-glm(ACR_response ~ GAUS + Gender + Age, family=binomial)
M1<-glm(ACR_response ~ Gender + Age, family=binomial)
anova(M1,M0, test="Chisq")
summary(M1)

```

Model performance

Discrimination, i.e. the model's ability to distinguish between the patients who will experience a response from those you will not, will be quantified with the measures sensitivity, specificity, and the concordance statistic, the *c*-index (i.e. the area under the receiver operating characteristic curve [ROC] in the case of binary outcomes)[50,51] The ROC curve is a plot of sensitivity (true positive rate) against one minus specificity (false positive rate) for consecutive cutoffs for the probability of experiencing a response.[52] The *c*-index is the probability, across all patients, that the model correctly predicts that one patient has a higher probability of experiencing a response compared to another patient, where 0.5 indicate predictions that are no better than chance.[50]

Protocol deviations

Some deviations from the original protocol were considered necessary for the current study in order to specify the statistical analyses and ensure feasibility and interpretability of the study results despite the exploratory approach.

Study design:

Protocol: The enrolment period will be from 17 September 2015 to 1 February 2017. Follow-up will be completed by 15 June 2017.

SAP: The enrolment period was extended to 1st of June 2017.

Rationale: To increase the study population as enrolment was more difficult than first expected. Ethical approval was obtained for extending the enrolment period (no. 55414).

Clinical examination:

Protocol: An Assessment of Motor and Process Skills (AMPS test) will be performed by a calibrated occupational therapist who has attended a specialised training course in the standardised AMPS administration procedures.

SAP: The AMPS was only performed on the initial 30 patients included in the study, and AMPS results will not be part of the proposed manuscript. Instead these will be reported in a separate paper (later on).

Rationale: Many patients considered the examination programme too long. As AMPS was time-consuming and not a central part of the study objective we decided to eliminate this part in order to ensure compliance.

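### Model performance does not name the model whose discrimination is reported and gives only 0.5 as reference, which does not isolate WP or GAUS if the adjusted models are meant

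*SAP*

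**What the plan says.** Under Analysis objectives, one stated aim is "to study the predictive value of pain profile and ultrasonographic scores on response" to treatment. Under Primary analyses, "Estimates will be reported from unadjusted and adjusted models", and because the sample is small "the models will only be adjusted for age (years) and gender (male/female"). Table 2 reports both versions side by side.

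The rationale for the two covariates is partly that they may themselves bear on the outcome. For gender, "it is possible that gender affects the odds of experiencing a treatment response"; a similar argument is made for age.

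Model performance then defines its target as "Discrimination, i.e. the model's ability to distinguish between the patients who will experience a response from those you will not", and this "will be quantified with the measures sensitivity, specificity, and the concordance statistic". The only benchmark on the c-index scale is the remark "where 0.5 indicate predictions that are no better than chance". The section does not identify the model. It sets no cut-off on predicted probability for sensitivity and specificity, and it plans no comparison of c-indices.

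The code under Programming fits the adjusted model, "M1<-glm(ACR_response ~ WP + Gender + Age, family=binomial"), and then a model with gender and age only. The second model is used only for a chi-square comparison.

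**The concern.** The c-index describes everything in the model. In the unadjusted WP or GAUS model that is the predictor of interest, so the result answers the study question. In the adjusted model it is age, gender and the predictor together. There, 0.5 corresponds to the three jointly carrying no information, not to WP or GAUS adding nothing.

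The SAP itself expects that age and gender may influence response. A c-index of 0.6 to 0.7 from the adjusted model could therefore be credited to the pain or ultrasound profile when the covariates produce it. Sensitivity and specificity taken from that model have the same difficulty. Because the model is not named, the choice of which c-index to report can also be made after the data are seen.

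**Working it through.** **Inputs.** From the SAP: the unadjusted and adjusted models, the age + gender model in the code, and 0.5 as the only reference. The SAP states no sample size, response rate, WP prevalence, covariate effect or expected c-index. There is thus no figure to reproduce, and every rate and effect in step 3 is an assumption. The simulations were run for WP; the algebra in steps 1 and 2 applies equally to GAUS.

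**Step 1: unadjusted model.** For a binary predictor with sensitivity Se and specificity Sp, counting ties as one half:

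c = Se·Sp + ½[Se(1 − Sp) + (1 − Se)Sp] = (Se + Sp)/2

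This equals 0.5 exactly when Se + Sp = 1, that is, when the predictor is uninformative. So 0.5 is the correct null value, and no probability cut-off is needed. In small samples a null WP still averaged 0.53 to 0.56 (n = 60 to 150) when its direction was taken from the data.

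**Step 2: adjusted model.** Split the distance from 0.5:

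c(full) − 0.5 = [c(age + gender) − 0.5] + [c(full) − c(age + gender)]

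Only the second bracket belongs to WP or GAUS. If the WP coefficient is zero, the second bracket is zero in the population, whatever the value of c(full).

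**Step 3: size under assumptions.**

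*Setting A.* 40% response, 55% women, WP in 45% of women and 25% of men, WP null given age and gender.

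| Gender OR | Age OR per SD | True c, full model | c in new patients, model fitted at N = 100 |
|---|---|---|---|
| 1.5 | 0.8 | 0.58 | 0.55 |
| 2 | 0.7 | 0.64 | 0.61 |
| 2.5 | 0.6 | 0.68 | 0.67 |

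The true c-index is the same with and without WP. WP alone gives 0.51 to 0.52. Over N = 70, 100 and 150 the mean apparent gain from adding WP was 0.006 to 0.021, and the likelihood-ratio test of WP rejected in 4% to 7% of runs. The new-patient column is free of in-sample optimism, so optimism is not what lifts these values above 0.5.

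*Setting B.* n = 80, about 35% response, WP in 40%, 55% women, 500 replicates. The values are mean apparent c-indices, and the gain is averaged before rounding.

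| WP OR | Female OR | Age OR per SD | c, age + gender | c, full | Gain |
|---|---|---|---|---|---|
| 1 | 1 | 1 | 0.581 | 0.606 | 0.024 |
| 1 | 0.5 | 0.7 | 0.653 | 0.668 | 0.015 |
| 1 | 0.4 | 0.6 | 0.697 | 0.709 | 0.012 |
| 1 | 0.33 | 0.5 | 0.733 | 0.742 | 0.009 |
| 0.33 | 0.4 | 0.6 | 0.679 | 0.737 | 0.057 |

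The last two rows make the point. A useless WP and a strong WP give nearly the same full-model c-index (0.742 and 0.737), and only the gain separates them (0.009 against 0.057). With n = 5000 and a null WP, the gain is 0.000 in all three settings with covariate effects (full-model c 0.635, 0.683, 0.724). The first row is pure overfitting, which is a separate issue but a reason to correct the difference for optimism.

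**Step 4: code.** In each adjusted block the second assignment to M1 (gender + age) overwrites the first (WP or GAUS + gender + age), and M0 is never defined. As printed, the comparison cannot run as intended, and a c-index taken from M1 afterwards would describe age + gender alone.

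**The case against.** The strongest reply is that the SAP already examines the separate contribution of WP and GAUS. The primary results are crude and adjusted odds ratios with a nested chi-square comparison, and Tables 2, 3, 4s and 5s have no column for a c-index. A reader shown a c-index would also see WP's adjusted odds ratio and p-value, and in the simulations a correctly coded test rejects a null WP only about as often as it should. This stands and limits the consequence. It does not supply a comparator on the discrimination scale, which the SAP chose to report as a result of its own.

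A reader might infer that the SAP measures discrimination on the adjusted model. It does not say so; it refers only to the model. The description of a ROC curve over successive probability thresholds suits a model with a continuous term such as age, since a binary predictor gives one interior point. That is a hint and not a statement.

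A reader might also infer that 0.5 is a decision threshold, and compute how often an interval for the c-index would clear it when WP is null. The SAP plans no interval, test or threshold for the c-index, and the remark about 0.5 explains the scale. Such error rates would belong to a rule that is not in the plan.

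Finally, the gain in c-index is itself optimistic in small samples. At N = 100 with a null WP, the apparent gain averaged 0.009 to 0.015 and the mean over refitted bootstrap samples 0.017 to 0.023, against a true value near zero. This stands, so an uncorrected difference would not be an adequate remedy.

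**Conclusion.** The point holds as a gap in specification: the model is not named, and the single reference value suits only the unadjusted models. If an adjusted model's c-index is reported against 0.5, it cannot show the predictive value of WP or GAUS. Under the setting A assumptions, a null WP leaves a true full-model c-index of about 0.58 to 0.68 with essentially no gain over age + gender. The exact size depends on the assumed covariate effects; the direction requires only that age or gender be related to response, which the SAP considers possible. The primary odds ratios are not affected, and the study is declared exploratory. This is a minor point about a supporting result.

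**What to change.** In Model performance:

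- Name the models whose discrimination is reported.
- Take the sensitivity, specificity and c-index of WP and of GAUS from the unadjusted models, with 0.5 as reference.
- For the adjusted models, report the c-index of age + gender, of age + gender + WP and of age + gender + GAUS. Give the optimism-corrected difference from age + gender with a bootstrap confidence interval, refitting both models in each resample.
- State that this is a descriptive supplement to the adjusted odds ratio and the likelihood-ratio test.

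In Programming, assign the gender + age model to M0 in both adjusted blocks, so that M1 keeps the full model.

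The cost is a few sentences and a few lines of R, with no new data. The downside is slightly more analysis and a discrimination result that will look less favourable than the full-model c-index.

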Appendix 1: Statistical analysis plan

Figure 1: Flow chart

[figure not shown]

Table 1: Baseline characteristics according to pain profile

Demographics and disease characteristics	Total (n=)	WP+ (n=)	WP - (n=)	Difference (95%CI)	P- value
Age, years					
Female, n (%)					
PsA duration, months					
PsA symptom duration, months					
Psoriasis duration, months					
Spinal involvement, n (%)					
Higher educational level ¹ , n (%)					
Smoking (current), n (%)					
Alcohol daily use, n (%)					
Body mass index, kg/m ²					
Medication					
csDMARD naïve, n (%)					
bDMARD naïve, n (%)					
Scheduled for csDMARD, n (%)					
Scheduled for bDMARD, n (%)					
Scheduled for cs+bDMARD, n (%)					
NSAIDs daily use, n (%)					
Mild analgetics daily use, n (%)					
Opioids daily use, n (%)					
Clinical and composite measures					
VAS physician (0-100)					
Swollen joint count (0-66)					
Tender joint count (0-68)					
SJ/TJ ratio <0.5, n (%)					
SPARCC enthesitis (0-16)					
DAS28CRP score (0-10)					
DAPSA score (0-164)					
Tender point count (0-18)					
PASI (if BSA >1) (0-72)					
Nail psoriasis, n (%)					
Dactylitis (0-20)					
Patient reported outcome measures					
VAS global (0-100)					
VAS Pain (0-100)					
PDQ score (-1 -38)					
MOS SF-36 MCS (0-100)					

MOS SF-36 PCS (0-100)

PsAID-12 (0-10)

DLQI (0-30)

NRS Fatigue (0-100)

GAD-10 (0-50)

BASFI (0-10)

BASDAI (0-10)

HAQ-DI (0-3)

Paraclinic assessments

Radiographic PsA, n (%)

CRP level, mg/L

Ultrasonography

GAUS (0-203)

GSAUS (0-204)

GCUS (0-312)

Table 3: Prognostic value of US and widespread pain profile on secondary outcomes

Predictors	n	n response (%)	Simple logistic regression		Multivariable, adjusted for age and gender	
			OR (95%CI)	P-value	OR (95%CI)	P-value
MDA						
Pain profile						
WP+			[Reference level]		[Reference level]	
WP-						
US profile						
GAUS =0						
GAUS >0			[Reference level]		[Reference level]	
DAPSA 50%						
Pain profile						
WP+			[Reference level]		[Reference level]	
WP-						
US profile						
GAUS =0						
GAUS >0			[Reference level]		[Reference level]	
PR-improvement						
Pain profile						
WP+			[Reference level]		[Reference level]	
WP-						
US profile						
GAUS =0						
GAUS >0			[Reference level]		[Reference level]	

GAUS, Global Acute Ultrasonic Score; WP; widespread pain; MDA, Minimal disease activity; DAPSA, Disease Activity Index for Psoriatic arthritis; PR-improvement; Patient reported improvement.

Figure 2: Scatter diagrams: Association between change in DAPSA and DAS28-CRP and baseline WPI and GAUS scores

- a) WPI score vs Δ DAPSA
- b) WPI score vs Δ DAS28
- c) GAUS vs Δ DAPSA
- d) GAUS vs Δ DAS28

Table 4: Change in the OMERACT PsA core set domains* from baseline to follow-up (ITT population)

PsA Core domains	All patients		Difference (95% CI)	P-value	GAUS=0	GAUS>0	Difference (95% CI)	P-value
	WP-	WP+						
MSK disease activity								
Δ SJC								
Δ TJC								
Δ SPARCC								
Δ BASDAI								
Skin disease								
Δ PASI								
Pain								
Δ VAS pain								
Δ SF-36 BP								
Physical Function								
Δ SF-36 PF								
Δ HAQ								
Δ BASFI								
HRQol								
Δ DLQI								
Δ PsAID								
Patient Global								
Δ Patient Global VAS								
Fatigue								
Δ NRS Fatigue								
Δ SF-36 VT								
Systemic inflammation								
Δ CRP								

*OMERACT PsA core domains set as updated and endorsed in 2016[3]

WP, Widespread pain; GAUS, Global Acute Ultrasonic score; CI, Confidence intervals; MSK, Musculoskeletal; SJC, swollen joint count; TJC, tender joint count; SPARCC, Spondyloarthritis Research Consortium of Canada enthesitis score; BASDAI, Bath Ankylosing Spondylitis Disease Activity Index; PASI, Psoriatic Area Severity Index; VAS, visual analogue scale; SF-36 BP, Medical Outcomes Study Short Form 36 Bodily Pain; PF; Physical Function; HAQ-DI, Health Assessment Questionnaire Disability Index; BASFI, Bath Ankylosing Spondylitis Functional Index; DLQI, DLQI, Dermatology Life Quality Index; PsAID, Psoriatic Arthritis Impact of Disease score; NRS, Numeric rating scale; VT; Vitality SFCRP, c-reactive protein.

Statistical Analysis Plan

Table 1s: Baseline characteristics according to ultrasound characteristics

Demographics and disease characteristics	n	GAUS > 0 (n=)	GAUS = 0 (n=)	Difference (95%CI)	P- value	n	GSAUS ≥ median (n=)	GSAUS < median (n=)	Difference (95%CI)	P- value	n	GCUS ≥ median (n=)	GCUS < median (n=)	Difference (95%CI)	P- value
Age, years															
Female, n (%)															
PsA duration, months															
PsA symptom duration, months															
Psoriasis duration, months															
Spinal involvement, n (%)															
Higher educational level ¹ , n (%)															
Smoking (current), n (%)															
Alcohol daily use, n (%)															
Body mass index, kg/m ²															
Medication															
csDMARD naïve, n (%)															
bDMARD naïve, n (%)															
Scheduled for csDMARD, n (%)															
Scheduled for bDMARD, n (%)															
Scheduled for cs+bDMARD, n (%)															
NSAIDs daily use, n (%)															
Mild analgetics daily use, n (%)															
Opioids daily use, n (%)															
Clinical and composite measures															
VAS physician (0-100)															
Swollen joint count (0-66)															
Tender joint count (0-68)															
SJ/TJ ratio <0.5, n (%)															

Statistical Analysis Plan

SPARCC enthesitis (0-16)

DAS28CRP score (0-10)

DAPSA score (0-164)

Tender point count (0-18)

PASI (if BSA >1) (0-72)

Nail psoriasis, n (%)

Dactylitis (0-20)

Patient reported outcome measures

VAS global (0-100)

VAS Pain (0-100)

PDQ score (-1 -38)

MOS SF-36 MCS (0-100)

MOS SF-36 PCS (0-100)

PsAID-12 (0-10)

DLQI (0-30)

NRS Fatigue (0-100)

GAD-10 (0-50)

BASFI (0-10)

BASDAI (0-10)

HAQ-DI (0-3)

Paraclinic assessments

Radiographic PsA, n (%)

CRP level, mg/L

Data are presented as mean (SD) unless otherwise stated. GAUS, Global Acute Ultrasound Score; GSAUS, Global Subacute Ultrasound Score; GCUS, Global Chronic Ultrasound Score. ¹Higher educational level refers to University degree (or similar), PsA, psoriatic arthritis; csDMARD, conventional synthetic disease modifying drugs; bDMARD, biologic disease modifying drugs; NSAID, Non-steroidal anti-inflammatory drugs; GCS, glucocorticoids; VAS, Visual Analogue Scale; SJ/TJ, swollen joints/tender joints; SPARCC, Spondyloarthritis Research Consortium of Canada enthesitis score; DAS28, Disease Activity Score using 28 joint and crp; DAPSA, Disease activity Index for psoriatic arthritis; PASI, Psoriatic Area Severity; PDQ, PainDETECT Questionnaire; MOS SF-36 MCS; Medical Outcomes Study Short Form 36 Mental Component Summary; MOS SF-36 PCS; Medical Outcomes Study Short Form 36 Physical Component Summary; PsAID, Psoriatic Arthritis Impact of Disease score; DLQI, Dermatology Life Quality Index; NRS, numeric rating scale; GAD-10, Generalized Anxiety Disorder; BASFI, Bath Ankylosing Spondylitis Functional Index; BASDAI, Bath Ankylosing Spondylitis Disease Activity Index; HAQ-DI, Health Assessment Questionnaire disability index; CRP, C-reactive Protein.

Statistical Analysis Plan

Table 2s: Baseline characteristics according to pain profile

Demographics and disease characteristics	n	PDQ < 13	PDQ ≥ 13	Difference (95%CI)	P-value	n	TPC < 8	TPC ≥ 8	Difference (95%CI)	P-value	n	SJ/TJ < 0.5	SJ/TJ ≥ 0.5	Difference (95%CI)	P-value
Age, years															
Female, n (%)															
PsA duration, months															
PsA symptom duration, months															
Psoriasis duration, months															
Spinal involvement, n (%)															
Higher educational level ¹ , n (%)															
Smoking (current), n (%)															
Alcohol daily use, n (%)															
Body mass index, kg/m ²															
Medication															
csDMARD naïve, n (%)															
bDMARD naïve, n (%)															
Scheduled for csDMARD, n (%)															
Scheduled for bDMARD, n (%)															
Scheduled for cs+bDMARD, n (%)															
NSAIDs daily use, n (%)															
Mild analgetics daily use, n (%)															
Opioids daily use, n (%)															
Clinical and composite measures															
VAS physician (0-100)															
Swollen joint count (0-66)															
Tender joint count (0-68)															
SJ/TJ ratio <0.5, n (%)											-	-	-	-	-
SPARCC enthesitis (0-16)															

Statistical Analysis Plan

DAS28CRP score (0-10)

DAPSA score (0-164)

Tender point count (0-18)

PASI (if BSA >1) (0-72)

Nail psoriasis, n (%)

Dactylitis (0-20)

Patient reported outcome measures

VAS global (0-100)

VAS Pain (0-100)

PDQ score (-1 -38)

MOS SF-36 MCS (0-100)

MOS SF-36 PCS (0-100)

PsAID-12 (0-10)

DLQI (0-30)

NRS Fatigue (0-100)

GAD-10 (0-50)

BASFI (0-10)

BASDAI (0-10)

HAQ-DI (0-3)

Paraclinic assessments

Radiographic PsA, n (%)

CRP level, mg/L

Ultrasonography

GAUS score

GSAUS score

GCUUS score

Data are presented as mean (SD) unless otherwise stated. ¹Higher educational level= University degree or similar. PDQ, PainDETECT Questionnaire; TPC, tender point count; SJ/TJ, swollen/tender joints; PsA, psoriatic arthritis; cs/bDMARD, conventional synthetic/biologic disease modifying drugs; NSAID, Non-steroidal anti-inflammatory drugs; VAS, Visual Analogue Scale; SPARCC, Spondyloarthritis Research Consortium of Canada enthesitis score; DAS28-CRP, Disease Activity Score, DAPSA, Disease activity Index for psoriatic arthritis; PASI, Psoriatic Area Severity; MOS SF-36 MCS/PCS Medical Outcomes Study Short Form 36 Mental/Physical Component Summary; PsAID, Psoriatic Arthritis Impact of Disease score; DLQI, Dermatology Life Quality Index; NRS, numeric rating scale; GAD-10, Generalized Anxiety Disorder; BASFI, Bath Ankylosing Spondylitis Functional Index; BASDAI, Bath Ankylosing Spondylitis Disease Activity Index; HAQ-DI, Health Assessment Questionnaire disability index; CRP, C-reactive Protein; GAUS, global acute ultrasound score; GSAUS, global subacute ultrasound score; GCUUS, global chronic ultrasound score.

Statistical Analysis Plan

Table 4s: Predictive value of US pathology and widespread pain profile on ACR20 response for the per protocol population (n=XX)

Predictors	n	n response (%)	Simple logistic regression		Multivariable, adjusted for age and gender	
			OR (95%CI)	P-value	OR (95%CI)	P-value
Primary						
Pain profile						
WP+			[Reference level]		[Reference level]	
WP-						
US profile						
GAUS =0						
GSAUS >0			[Reference level]		[Reference level]	

GAUS, Global Acute Ultrasonic Score; WP; widespread pain, CI, confidence intervals

Table 5s: Predictive value of US pathology and widespread pain profile on ACR20 response using the 'as observed' population (n=XX)

